Exercise training is a proven effective treatment for patients with PAD with significant functional, psychosocial and economic benefits. In current practice, there are no guidelines for exercise training and rehabilitation for patients who have progressed to CLI and have undergone revascularization. While it may be a challenge given the severity of disease and number of comorbidities in this patient population, it is great a disservice to deny these patients exercise rehabilitation given the possible advantages for their functional capacity, quality of life and even survival. Randomized controlled trials (RCT) are necessary to determine the precise role of exercise rehabilitation in patients with CLI. An RCT will provide guidance for regarding exercise tolerance, appropriate exercise modalities as well as the challenges and benefits of exercise rehabilitation in this critically ill population.

Objectives:

The aim of this pilot study is to develop a better understanding of the role for supervised exercise rehabilitation programs (SEP) in CLI patients after revascularization.

Our key objectives are as follows:

- 1) Our primary objective is to show that a 12-week SEP will improve functional capacity and quality of life in patients with CLI after revascularization. We will assess the feasibility for completion of a 12-week SEP in patients with CLI who have undergone revascularization.
- 2) Our secondary objective is to monitor major adverse limb events (MALE) and survival in patients who complete a 12-week SEP after revascularization.

Hypotheses:

- 1) We hypothesize that PAD-CLI patients who participate in an exercise rehabilitation after they have undergone revascularization will have a greater improvement in functional capacity and quality of life compared with patients treated with best medical therapy alone.
- 2) We hypothesize that PAD-CLI patients who participate in an exercise rehabilitation after they have undergone revascularization will have fewer MALE and improved survival compared with patients treated with best medical therapy alone.

OUTCOME MEASURES:

Primary outcome measures:

Our primary outcome measure for this project will be change in functional capacity as measured by a 6-minute walking test (6MWT) or maximal pain-free walking distance on a treadmill.

Secondary outcome measures:

- 1) Quality of life based on questionnaires validated for patients with PAD, the SF-36 and VQ6
- 2) Completion of a 12 week supervised exercise program

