- 2) Freedom from MALE
- 3) Target vessel and/or bypass patency
- 4) Survival at 1, 3 and 5 years

STUDY DESIGN

This study is a two phase, single-center, non-blinded randomized controlled trial. The first phase of the trial will include 20 patients; 10 assigned to post-operative exercise rehabilitation and 10 to best medical therapy. The primary objective of Phase I is to assess for feasibility and safety of this randomized controlled trial in CLI patients after revascularization. We will assess rate of enrollment, adherence to the exercise regimen and any unforeseen barriers or challenges that patients may encounter with the rehabilitation program.

If Phase I of the trial confirms that the exercise program is feasible and safe for CLI patients post-revascularization, we will proceed with Phase II of the trial. The primary objective for Phase II is to determine if a supervised exercise rehabilitation program will improve walking distance after revascularization compared with patients treated with best medical therapy. Phase II will also compare quality of life outcomes between the two groups.

STUDY POPULATION

The population to be studied in this group is patients with PAD and CLI Fontaine classification III and IV. This means that these patients will have ischemic rest pain in their legs and/or non-healing ischemic ulcers on their feet.

ENROLLMENT

Patients will be identified on a referral basis through our outpatient vascular surgery clinic. The seven practicing vascular surgeons in Calgary will be informed of the current study. Patients who have undergone revascularization for CLI will be identified for consideration of participation in this study within six months of their procedure. All surgical and ischemic wounds to be deemed sufficiently healed prior to assessment for fitness in the study. Once the attending vascular surgeon considers the patient fit to participate, the research coordinator will assess the patient for possible inclusion in the study.

Inclusion Criteria

- 1) Ambulating prior to procedure
- 2) Living independently prior to procedure
- 3) Available to attend all SEP and follow-up appointments
- 4) PAD Fontaine class III and IV (rest pain and tissue loss)
- 5) Entry with consent of vascular surgeon
- 6) Ischemia secondary to TASC A-D lesions identified on imaging (CTA or angiogram)
- 7) Able to understand and sign informed consent
- 8) >18 years of age

Exclusion Criteria

- 1) Confined to wheelchair

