- 2) Patients with exercise tolerance limitations due to other co-morbidities such as cardiorespiratory, musculoskeletal, or peripheral neuropathy. (NYHA class III and IV)
- 3) PAD Fontaine class I and II (asymptomatic, claudication)
- 4) Patients with ongoing tissue loss that limits ambulation
- 5) Patient with previous revascularization procedures
- 6) Patients undergoing revascularization for acute limb ischemia events

SAMPLE SIZE

There are currently no data evaluating outcomes of post-revascularization supervised exercise programs in patients with critical limb ischemia, however these studies have been completed in claudication

patients. Studies on PAD claudication (Fontaine class II) patients who have undergone revascularization followed by SEP have all shown significant improvement in functional capacity compared with best medical therapy alone. These previous studies that showed consistently a 20% greater increase in walking distance in the post-revascularization SEP group compared with Best Medical Therapy (BMT) post-revascularization. Given this previous data, 64 patients are required to have a 80% chance of detecting, with a two-sided significance of 0.05, an increase in the primary outcome measure of a 20% greater increase in distance for the 6MWT in the experimental group compared with the control group. Final sample size will be adjusted for expected attrition.

METHODS

INTERVENTION

Patients included in the study will be identified in the vascular surgery outpatient clinic or through Emergency department as requiring revascularization secondary to critical limb ischemia. Patients will be approached regarding study participation prior to the revascularization procedure. After eligibility is confirmed and patients have signed informed consent, patients will be randomized to one of two groups:

- 1) Best Medical Therapy (BMT)
- 2) BMT + Supervised Exercise Program (SEP)

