The patient will undergo the revascularization procedure and any adjunctive treatment such as wound care/debridement or minor amputation (toes, trans-metatarsal amputation). All surgical wounds and ischemic ulcers will require assessment by attending surgeon for adequate healing prior to initial assessment at the exercise facility. This may require as little as one week or as long as 6 weeks to achieve sufficient healing. The exercise assessment and program delivery will take place at a cardiac rehabilitation facility that has extensive experience in managing patients with cardiovascular disease and PAD in the post op setting.

Best medical therapy

All patients in the study will be assessed and monitored by internal medicine specialists as well as the vascular surgery team for management of PAD risk factors including, but not limited to: hypertension, smoking cessation, dyslipidemia and diabetes. The patients will be prescribed appropriate pharmacotherapy as deemed appropriate. A typical regimen for these patients may include antiplatelet agents, B-blockers, ACE-inhibitors, and diabetic control agents. Patients will be advised to target a systolic blood pressure of $\leq 140\text{mmHg}$ ($\leq 130\text{mmHg}$ if diabetic), $\text{LDL-C} < 2.0\text{ mmol/L}$ and a $\text{HbA1c} \leq 7\%$. They will also be given information regarding engaging in exercise and physical activity three to five times per week. Patients will be asked to keep a log of their physical activity for the 12-week duration of the study. The patients will be provided with a log to record their physical activity.

Standardized Exercise Program Regimen

In addition to best medical therapy management, the patients randomized to the SEP arm of the trial will attend a supervised exercise program at a cardiac rehabilitation facility at least two times per week for 12 weeks. Programs will be designed and coordinated by an exercise physiologist. All patient expenses for the program will be covered by the study budget. There will be no financial burden placed on the participants.

MEASUREMENTS

General health metrics will be collected at the start and end of the 12-week intervention period. This includes height, weight, BMI, blood pressure and resting heart rate. We will record medications,

smoking history status, presence of diabetes, dyslipidemia, cardiovascular disease history including previous myocardial infarct (MI) and stroke/transient ischemic attack.

PRE/POST TESTING

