Microsoft Excel will be used to generate a block randomization sequence for Phase I (20 patients) followed by a block randomization sequence for Phase II (44 patients) of the study. Patients who are eligible to participate in the study will be stratified by sex and randomized to either SEP or BMT. Block sizes of 4 and 6 will be used to prevent anticipation of the randomization sequence.

ALLOCATION CONCEALMENT

Once the random block sequence has been generated, allocation cards will be created and sealed in sequentially numbered opaque envelopes. The envelopes will be stored in a secured filing cabinet in the vascular surgery research office. The envelopes will be opened sequentially after a patient consents to participate in the study.

DATA COLLECTION

No study data will be collected until patients have reviewed and signed the informed consent. Opportunity to ask questions and have time independent from study team will be provided.

Data will be recorded using Excel spreadsheets. Medical outcomes and complications will be tracked using Vascubase software. Data will be stored on Alberta Health Services computers to maintain patient confidentiality.

STATISTICAL ANALYSIS

Normally distributed data will be presented as mean \pm SD. Results at baseline and 12 weeks will be compared using a paired t-test. For data that is not normally distributed, comparisons will be performed using a non-parametric Mann-Whitney test. Comparisons will be accepted as statistically significant at 95% confidence level ($p \leq 0.05$). STATA software will be used for statistical analysis.

ETHICAL CONSIDERATIONS

Patients who are randomized to the SEP group will be provided with tri-weekly visits for supervised exercise guidance and support. Patients will receive reimbursement for travel to and from the exercise facility. This will include refunds for gas, parking or other required transportation (taxi, public transport, etc).

FOLLOW UP OF PATIENTS WITHDRAWN FROM STUDY

Patients who withdraw or do not complete the program will be contacted and interviewed at the end of the 12 week study period to understand why they were unable to complete the training program.

LIMITATIONS

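### The analysis plan names no test of supervised exercise against best medical therapy for normally distributed outcomes; its paired t-test answers a different question

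*Combined protocol and SAP*

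**What the plan says.** The Statistical Analysis section is a few sentences long and does not mention arms or groups. For normally distributed data: "Results at baseline and 12 weeks will be compared using a paired t-test". For the rest: "For data that is not normally distributed, comparisons will be performed using a non-parametric Mann-Whitney test". No unpaired t-test, ANCOVA or mixed model appears there or in any other section.

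The questions the trial sets itself are between-arm:

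- Hypotheses: exercise patients "will have a greater improvement in functional capacity and quality of life compared with patients treated with best medical therapy alone".
- Study Design: walking distance under SEP is set against BMT in Phase II, and "Phase II will also compare quality of life outcomes between the two groups".
- Sample Size: 64 patients, 80% power, two-sided 0.05, for a "20% greater increase in distance for the 6MWT in the experimental group compared with the control group".

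Two other places bear on the point. Under Best medical therapy, which applies to every patient: "They will also be given information regarding engaging in exercise and physical activity three to five times per week". On the order of events, Intervention says "Patients will be approached regarding study participation prior to the revascularization procedure" and randomises once consent is signed, whereas Enrollment says "Patients who have undergone revascularization for CLI will be identified for consideration of participation in this study within six months of their procedure".

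**The concern.** A before/after test within patients cannot separate an SEP effect from anything else that improves walking over the 12 weeks. Here that includes continuing recovery after revascularisation, risk-factor management, and the exercise advice given to both arms. The control arm exists to remove those influences, and the named test makes no use of it. The section also does not say whether the paired test is run within each arm or over all patients together.

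The Mann-Whitney sentence does not close the gap, because it does not say what is compared:

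- If it means baseline against 12 weeks, an independent-samples test is being applied to paired data.
- If it means SEP against BMT, a normality check decides whether the trial answers the between-arm question or the change-over-time question.

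At stake is the efficacy conclusion of Phase II, or of both phases pooled. A significant rise in the SEP arm could be reported as benefit when the BMT arm rose as much. In a non-blinded trial, leaving the between-arm test unnamed also leaves the choice among final values, change, percent change or ANCOVA to be made after the data are seen.

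**Working it through.** **The plan's own figure.** The 64 cannot be reproduced, because no SD is given. The randomisation section splits it as 20 + 44 = 64. Equal arms are stated for Phase I and assumed overall, giving 32 per arm. For a two-sample comparison the implied standardised difference is (1.960 + 0.842) × √(2/32) = 0.700. A 20-point difference in percent change then implies an SD of 20/0.700 = 28.6 points. The sample size is framed as a between-arm comparison, and the analysis section contains no matching test.

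**How the paired test behaves when SEP does nothing.** Suppose both arms gain the same k SDs of the change. The documents give no k, so a range is used. For n pairs the t statistic is noncentral t with n − 1 df and noncentrality k√n. Example: n = 32, k = 0.35 gives 0.35 × 5.657 = 1.98 against a critical value of 2.04, so the test is significant 48% of the time.

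Probability (%) of p ≤ 0.05, no SEP effect:

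| Shared gain k | 0 | 0.05 | 0.1 | 0.2 | 0.35 | 0.5 | 0.7 |
|---|---|---|---|---|---|---|---|
| SEP arm, n = 32 (phases pooled) | 5 | 5.9 | 8.5 | 19.5 | 48 | 78 | 97 |
| SEP arm, n = 22 (Phase II alone) | 5 | 5.6 | 7.3 | 14.6 | 35 | 61 | 88 |
| All patients, n = 64 | 5 | 6.8 | 12.4 | 35 | 79 | 98 | 100 |
| All patients, n = 44 | 5 | 6.2 | 9.9 | 25 | 62 | 90 | 99.5 |

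The 5% at k = 0 is two-sided; significant improvement alone is 2.5%. These are chances of detecting a real change over time. They are not the error rate of a decision rule in the plan.

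**Reading the two arms side by side.** If p is the chance of significant improvement in one arm, the pattern of SEP significant and BMT not has probability p(1 − p). For k = 0.35 and n = 32 this is 0.483 × 0.517 = 25%.

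| Shared gain k | 0 | 0.05 | 0.1 | 0.2 | 0.35 | 0.5 | 0.7 |
|---|---|---|---|---|---|---|---|
| 32 per arm (%) | 2.4 | 4 | 7 | 16 | 25 | 17 | 3 |
| 22 per arm (%) | 2.4 | 4 | 6 | 12 | 23 | 24 | 11 |

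**Between-arm tests under the same null.** A t-test of change, a Mann-Whitney test of change and ANCOVA were simulated with 10,000 trials per scenario. Scenarios covered 32 and 22 per arm, shared gain 0, 0.35 and 0.7 SD, baseline-to-12-week correlation ρ of 0.4, 0.6 and 0.8, and normal and lognormal data. Rejection stayed between 4.3% and 5.5%.

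**Mann-Whitney used for baseline against 12 weeks.** With 32 patients and no change, simulated rejection is 0.8% at ρ = 0.5 and 0.02% at ρ = 0.8. It is far too conservative to stand in for a paired test.

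**Choosing among valid tests.** With equal variances at the two times, the ratio of ANCOVA to change-score variance is (1 − ρ²) / [2(1 − ρ)] = (1 + ρ)/2, which is 0.70, 0.80 and 0.90 at ρ = 0.4, 0.6 and 0.8. For an assumed effect of 0.5 SD of the walk distance, simulated power (20,000 trials) at those three values of ρ is:

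| | ANCOVA (%) | t-test of change (%) |
|---|---|---|
| 32 per arm | 56 / 68 / 90 | 44 / 60 / 88 |
| 22 per arm | 41 / 50 / 75 | 31 / 43 / 73 |

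The effect size is an assumption. At ρ = 0.6 and 32 per arm, ANCOVA power runs from about 32% to about 93% as the effect goes from 0.3 to 0.7 SD.

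**The case against.** The fairest defence is that the between-arm intent is plain from the hypotheses, objectives and sample size, that the trial calls itself a pilot with feasibility first, and that the Mann-Whitney test, being for independent samples, was probably meant for SEP against BMT. Even on that reading it covers only non-normal data, so the gap for normal data remains. The pilot label does not help, because the protocol states a powered efficacy comparison. It does limit the point to the efficacy analysis.

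A second objection concerns size, and part of it stands. The highest figures measure power to detect a real change over time. A reader with a control arm in view would more likely compare the two within-arm results, and that pattern misleads in at most about 25% of null trials at the gains tabulated, falling to 3% at a gain of 0.7 SD with 32 per arm. Moreover, walking is first tested after the procedure and after wound healing has been judged adequate, so some recovery precedes baseline. Nothing in the documents supports any particular gain.

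A third objection also stands in part: ANCOVA of distance estimates a difference in metres, whereas the sample size is expressed as a percentage. The scale has to be aligned when the test is named.

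**Conclusion.** The point holds, and it must be fixed before any Phase II efficacy analysis. Followed as written, the plan gives a normally distributed primary outcome no test of the trial's own hypothesis. That conclusion comes from the text alone and needs no assumption.

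The size of the consequence does rest on assumptions: equal arms, approximately normal changes, and an unknown gain shared by both arms. Between shared gains of 0.2 and 0.5 SD, with no SEP effect and 32 per arm, the SEP-arm paired test is significant in roughly a fifth to four fifths of trials. With no shared gain it keeps its nominal level. Any of the three between-arm tests examined would repair the defect; preferring ANCOVA is a matter of precision. Phase I's feasibility and safety assessment is not affected.

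**What to change.** Replace the paired t-test sentence with a named between-arm analysis. Suggested text:

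> The primary analysis is an ANCOVA of 12-week 6MWT distance on randomised arm, adjusted for baseline 6MWT and sex, and for phase if Phases I and II are pooled. The adjusted SEP-minus-BMT difference is reported with its 95% CI and tested at two-sided 0.05. A Mann-Whitney test of change between arms is the sensitivity analysis. A normality check does not choose the primary method. Within-arm changes are descriptive. SF-36 and VascuQol are compared between arms in the same way.

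A two-sample t-test of change is an acceptable, less precise alternative.

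Settle these at the same time:

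- **Outcome and scale.** The sample size uses the 6MWT, but the primary outcome is worded as 6MWT or treadmill distance. Align the two, and say whether the target difference is in metres or percent.
- **Baseline.** The Functional Capacity section places the first walking test at the first exercise session, yet BMT patients have no supervised sessions scheduled. Tie it to the initial assessment in both arms, before any exercise session. Under the Intervention section this still falls after open-label randomisation, so that limitation should be stated.
- **Order of recruitment.** Enrollment and Intervention disagree on whether patients enter before or after revascularisation, and must be reconciled.
- **Missing tests.** State how patients without a baseline or 12-week walk are handled.

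Naming the test is analysis wording and needs no extra patients or procedures. The baseline rule adds no visit provided the initial assessment is already planned for BMT patients, which the protocol should confirm.

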A recent systematic review reports a global estimate of 202 million people living with PAD as of 2010 (Fowkes et al., 2013). Previously thought to be predominant in high income countries, this systematic review suggests that almost 70% of people suffering from PAD reside in lower and middle income countries. This systematic review compared global prevalence of PAD between 2000 and 2010 which showed a global increase in PAD of approximately 23.5%. The data show that PAD generally affects men and women at similar rates, with a slightly higher prevalence in women at older ages. This differs from previous works that suggested higher rates among men than women. The prevalence of PAD increases with increasing patient age, with a sharp rise in numbers ≥ 70 years of age (Criqui & Aboyans, 2015).

An elegant and powerful comment written by Hirsch and Duval (2013) describe PAD as a global pandemic given that it affects more than 200 million people worldwide. PAD greatly affects people's quality of life with a high degree of morbidity and mortality making this an important and relevant area of research. To put in context, as of 2011 approximately 34 million people were living with HIV. By comparison, PAD has a higher prevalence, morbidity and mortality compared with HIV (Hirsch & Duval, 2013).

Patients with CLI are the focus of this study. Although the incidence is clear, it is estimated that in Europe and North America there are 500-1000/1 million new cases of CLI every year. These patients exhibit the most severe form of the disease with guarded prognoses. At one year, there is a 10-40% mortality rate and up to 40% amputation rate in patients with critical limb ischemia. Only 45% of patients are alive with two limbs one year after a diagnosis of CLI (Hirsch et al., 2006; Norgren et al., 2007). These patients tend to be in extremely poor health with multiple comorbidities that are further outlined below.

Risk Factors

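### The 12-week walking result leaves out patients who die or have a major amputation, and the plan does not say how to bring them in

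*Combined protocol and SAP*

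**What the plan says.** The Statistical Analysis section gives one rule for normally distributed results: "Results at baseline and 12 weeks will be compared using a paired t-test". It gives a Mann-Whitney test for other data. It defines no analysis population and has no rule for a missing 12-week walk, death, major amputation or loss of ambulation.

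On patients who stop, the follow-up section says: "Patients who withdraw or do not complete the program will be contacted and interviewed at the end of the 12 week study period". The stated purpose is to learn why they stopped. No outcome value or analysis rule follows from the interview.

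Freedom from major adverse limb events (MALE) and survival are secondary outcomes. The second hypothesis is that supervised exercise (SEP) will reduce limb events and improve survival. The secondary objective, however, is worded for patients who finish the programme.

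The Epidemiology section describes a very sick population: "Only 45% of patients are alive with two limbs one year after a diagnosis of CLI". The Sample Size section says that "64 patients are required to have a 80% chance of detecting, with a two-sided significance of 0.05", for "a 20% greater increase in distance for the 6MWT in the experimental group compared with the control group". It promises an adjustment for attrition but gives no rate.

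**The concern.** A patient without a second walk cannot enter a paired test. The Mann-Whitney alternative has the same gap until someone decides what value a patient who has died or lost a leg should take.

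These losses are not like a missed appointment. They are the worst outcomes a walking trial can record, and the trial expects its treatment to change how often they happen. If it does, in either direction, the patients left at 12 weeks are no longer the groups that were randomised. The primary result would then answer a narrower question, about those who survived and could still walk, without saying so.

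The trial is unblinded. A rule chosen after losses by arm are known would not be credible.

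**Working it through.** **1. The plan's own figure.** The phases ("block randomization sequence for Phase I (20 patients) followed by a block randomization sequence for Phase II (44 patients") add to 20 + 44 = 64, so 64 is the total. Taking 32 per arm assumes 1:1 throughout, as in Phase I ("10 assigned to post-operative exercise rehabilitation and 10 to best medical therapy"). Reading the target as a difference of 20 percentage points, n per arm = 2 × (1.96 + 0.842)² × (SD/20)² = 15.7 × (SD/20)². An SD of 28.5 gives 15.7 × 2.03 = 31.9, so 32 per arm. The plan states no SD, and 64 can be neither confirmed nor refuted. SD 28.5 is used below only as the value consistent with 64.

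**2. Death or limb loss over the trial window.** Two sources in the document:

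- *Epidemiology, 45% alive with two limbs at one year, constant rate.* By 12 weeks: 1 − 0.45^(12/52) = 16.8%. Counting from the procedure, with 1 to 6 weeks of healing before the first session (Intervention section), by 13 weeks: 1 − 0.45^(13/52) = 18.1%; by 18 weeks: 1 − 0.45^(18/52) = 24.1%.
- *Table 2, angioplasty, death and limb loss assumed independent.* From the six-month figures at a constant rate: 1 − (0.882 × 0.923)^(12/26) = 9.1%. But losses come early: 1 − 0.934 × 0.983 = 8.2% by one month. Log-linear interpolation between 1 and 6 months gives 1 − 0.915 × 0.961 = 12.0% by 12 weeks and 14.9% by 18 weeks. Counting 12 weeks from month 1 gives 1 − 0.969 × 0.966 = 6.4%.
- *Table 2, bypass.* Limb loss alone is 6.4% by 12 weeks and 7.6% by 18 weeks. Survival is not given.

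The range is about 6 to 24%, or 32 × 0.064 = 2 to 32 × 0.241 = 8 patients per arm.

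**3. Effect on power** (SD 28.5, two-sided 0.05, starting from 80%):

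| Loss | Power left | Total needed for 64 evaluable |
|---|---|---|
| 6% | 78% | 64/0.94, so 69 |
| 17% | 73% | 64/0.832, so 77 |
| 24% | 69% | 64/0.76, so 85 |

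**4. Can loss alone produce a false result?** Simulation with no true effect, 32 per arm, SD 28.5; all loss patterns are assumed.

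- Two lost in each arm: no mean bias between arms. The within-arm paired test, which is the one the plan names, is falsely significant for improvement in about 13% of trials if the lost patients are exactly those with the worst change, and about 5% if loss correlates 0.5 with change (nominal 2.5%).
- Five lost under SEP and two under best medical therapy (BMT): a between-arm test of completers falsely favours SEP in 12% and 5% of trials respectively.
- In a separate set-up (baseline 300 m, SD 80, correlation 0.7), loss of 17% against 5% tied to the baseline or 12-week walk, and not to the change, gives about 1.5 to 4%, close to nominal.

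**5. Two different questions.** Same 300 m set-up, with walkers under SEP truly gaining 40 m. At 17% against 5% loss, a completers-only between-arm test favours SEP in about 60 to 73% of trials, depending on how loss is modelled. A Mann-Whitney test on all 64, with lost patients ranked lowest, does so in about 17 to 24%. At equal 10% loss the figures are about 67% and 50%. The first test asks whether surviving walkers gained; the second, whether randomised patients fared better overall.

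**6. What rule should govern the claim?** In the 17% against 5% scenario, holding back a claim only when the two analyses point in opposite directions would stop about 3% of the significant completers results. Requiring the all-randomised analysis also to favour SEP at the stated level is much stricter: it does so in only about 17 to 24% of trials.

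**The case against.** The strongest reply has four parts.

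- *The quoted test compares time points, not arms.* This is correct. No SEP-against-BMT test is named for normally distributed data, which is a more basic gap. Filling it would not settle how deaths and amputations enter, so both need attention.
- *The one-year figures do not fit this trial.* A reader might infer from them that death and amputation will be common by week 12. The documents do not support that. The 45% figure is for critical limb ischemia generally, from diagnosis. This trial takes patients who walked and lived independently before the procedure, requires adequate wound healing, and excludes NYHA III and IV. Losses before the first exercise session cannot be caused by exercise. The low end of 6 to 24% is the more plausible part, although early losses still remove a patient from any change score.
- *Nothing shows that SEP will lose more patients.* A reader might take the 17% against 5% scenario as expected harm, or its gap as evidence of false positives. It is neither. The trial hypothesises the opposite direction, and the scenario assumes a real 40 m gain, so most of the gap separates two estimands. Material inflation between arms appeared only when unequal loss tracked the change in walking itself.
- *The events are recorded elsewhere.* This is true. They leave the walking comparison, not the trial. But a reader of the primary result is not told that its denominator depends on them.

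**Conclusion.** The concern holds in limited form. Followed as written, the primary walking result covers only patients with both walks, and the plan has no rule for those who die or have a major amputation first. The likely size is 2 to 8 of 32 per arm, probably nearer 2. That costs little power at the low end, but with arms this small a difference of a few patients can change what the result means. Equal loss gives no mean bias between arms, and the direction of any imbalance is unknown.

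This rests on 1:1 allocation throughout, an SD inferred and not stated, independence of death and limb loss in Table 2, and a patient with a major amputation not completing a 12-week walk. The window is itself uncertain: the Enrollment section identifies patients after the procedure, within six months, while the Intervention section approaches and randomises them before it. The two must be reconciled. The point should be settled before any data by arm are seen; it does not undermine the design.

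**What to change.** In the Statistical Analysis section:

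1. Name a between-arm comparison of change in 6MWT as the main analysis.
2. Prespecify a supporting analysis of all randomised patients: death before week 12 ranks lowest, then major amputation, then change in 6MWT, compared by the Mann-Whitney test already named. Minor amputation should not count, because the Intervention section allows it as adjunctive treatment.
3. State how a patient who is alive without major amputation but lacks a walk is handled, including one who never reached the first session. Without this the supporting analysis is not truly of all randomised patients.
4. Report deaths, major amputations and other missing walks by arm beside the 6MWT result.
5. State the claim rule: if the all-randomised analysis does not also favour SEP at the stated significance level, limit any claim to patients able to walk at 12 weeks.

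*Cost.* No new visits or patients. Survival and limb events are already followed, but the protocol's description of MALE also covers readmission and reintervention, so major amputation must be recorded separately with its date. The real price is power. At equal 10% loss and an assumed 40 m gain, the supporting analysis succeeds about 50% of the time against 67% for the completers' test, so an unrestricted claim would fail about half the time even if exercise works and harms no one. That is why it is proposed as supporting and not primary.
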